10. DIRECT ACCESS TO SOURCE DATA/DOCUMENTS

The Investigator or the organization involved in the study must allow direct access to the source data/documents for study-related monitoring, auditing, ethical expertise, and inspection carried out by authorized agencies.

Translated from Russian to English, dated 06-Jul-2020

11. QUALITY CONTROL AND QUALITY ASSURANCE OF THE STUDY CONDUCT

11.1. Quality guarantees

In accordance with ICH GCP and regulatory requirements, the Sponsor, third parties on its behalf, regulatory authorities or Ethics Committees can conduct audits (inspections) to ensure quality at any time during the study or after the end of the study. The Investigator must provide the auditors direct access to all study-related documents, including source documents, and allocate his/her time and time of his/her team to discuss with auditors the results of audits and inspections, as well as other issues.

11.2. Investigator's adherence to protocol

No deviations from the Protocol are allowed during the study without prior written permission from JSC BIOCAD, except when necessary to prevent any immediate danger to the volunteer.

Protocol deviation is any change, discrepancy, or deviation from the study design or procedures of the study Protocol.

Any protocol deviation in the course of the clinical study must be registered and reflected in the study documents.

All protocol deviations are classified as major or minor deviations.

A minor deviation from the Protocol is an unforeseen and unintended event that occurred during the study and contradicts the requirements of the Protocol, which does not significantly affect the rights, safety and well-being of the volunteer or the consistency, accuracy and reliability of the study data.

A major deviation from the Protocol (or a protocol violation) is a deviation that may affect the rights, safety of a volunteer or the consistency, accuracy, and reliability of the study data.

Examples of probable major protocol deviations:

- A volunteer met study exclusion criteria but was not excluded;
- A volunteer received a prohibited concomitant medication;
- A volunteer was included in the study without meeting the eligibility criteria;
- Study procedures were conducted without obtaining a written informed consent from a volunteer;

Translated from Russian to English, dated 06-Jul-2020

- Volunteer’s indiscipline, non-compliance with restrictions during participation in the study (taking alcohol, drugs);
- Errors in selection of doses/route of administration/drug storage;
- Protocol violations that may be considered by the clinical trial monitor or study coordinator to have an impact on the safety of participants or the consistency and reliability of the study data;
- Missing two or more of the scheduled blood samples for analysis of pharmacokinetics/pharmacodynamics;
- Any violation of the confidentiality of information about study participants.

Information about major deviations should be presented to the Sponsor and the local ethics committee. In case of any major protocol deviations, the volunteer must be excluded from the final PK/PD data analysis.

The Investigator must have enough time to conduct the study correctly and complete the study within the timeline agreed with JSC BIOCAD, and also have a sufficient number of qualified team members and adequate equipment to perform the procedures specified in this Protocol.

Each co-investigator involved in the study must be familiarized with the Protocol requirements and his/her responsibilities in the study. Delegation by the Principal Investigator of any of his/her responsibilities within this study must be documented in written form in the relevant section of the Investigator's File.

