4.6.3.15. Unscheduled visits

If adverse events occur, the volunteer may come for an unscheduled visit to conduct additional safety tests which should mandatorily include data collection on concomitant medication, physical examination, BP, body temperature measurements, complete blood count, blood biochemistry, urinalysis, and/or other tests deemed necessary by the Investigator.

4.7. Description of Interruption Rules or Early Withdrawal Criteria for individual subjects, study parts, or the study in general

Volunteers will be excluded from further participation in the study in the following cases:

1. Identification, after the volunteer's inclusion in the study, of gross violations of inclusion/non-inclusion criteria (as decided by JSC BIOCAD)⁵;
2. Patient's withdrawal of the consent to participate in the study;
3. AEs and SAEs, laboratory abnormalities or concomitant diseases, when, in the opinion of the investigator or Sponsor, the continuation of the study treatment is impossible or dangerous for the volunteer, or is not in the best interests of the volunteer, or is unsafe;
4. The volunteer misses more than 1 doses of BCD-089 (in this case, the withdrawal of such a patient will have to be agreed with representatives of JSC BIOCAD);
5. The patient has a major depressive disorder or suicidal ideation or makes suicidal attempts;
6. If the study is terminated by the decision of JSC BIOCAD, local Ethics Committee, or regulatory bodies;
7. In case of the use of drugs prohibited by the Protocol;

⁵Deviations from the eligibility criteria, which are justified by the Investigator and agreed by the Sponsor, are not a reason to exclude the patient from the study.

Translated from Russian to English, dated 06-Jul-2020

8. In case of the volunteer's death.

The Investigator has to inform JSC BIOCAD about the volunteer's premature withdrawal and the reasons of premature withdrawal within 24 hours.

If a volunteer is withdrawn from the study, the Study Completion Form in the CRF must be completed. Follow-up procedures of prematurely withdrawn patients are described in Section 5.4.

See Section 11.5 "Study Termination" below for further details.

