9.7 Patient selection for analysis

Demographic data and baseline clinical and laboratory characteristics will be evaluated in all volunteers included in the study.

Safety analysis

Safety analysis will include all volunteers who received the test drug.

Pharmacokinetic analysis

Pharmacokinetics analysis will include data from volunteers who have received BCD-089 and have had no more than two missing/lost/damaged blood serum samples for pharmacokinetics and had no more than two consecutive missing/lost/damaged samples and for whom a serum sample obtained before the test drug administration is available for the analysis.

Pharmacodynamic analysis

Pharmacodynamics analysis will include data from volunteers who have received BCD-089 and have had no more than two missing/lost/damaged of whole blood and/or blood serum for pharmacodynamics studies, and for whom a serum sample obtained before the test drug administration is available for the analysis.

Immunogenicity analysis

Immunogenicity analysis will include data from volunteers who have received BCD-089 and have not had missing/lost/damaged serum samples taken on Days 1 and 71 of the study.

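### Section 11.2 drops PK/PD data for any major deviation, even one unrelated to exposure, and so gives different PK and PD analysis sets from section 9.7

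*Combined protocol and SAP*

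**What the plan says.** Section 11.2 splits protocol deviations into minor and major. A major one "is a deviation that may affect the rights, safety of a volunteer or the consistency, accuracy, and reliability of the study data". Under the label "Examples of probable major protocol deviations" it gives a list. Some items bear directly on exposure, such as dosing, route or storage errors and prohibited medication. Others include "A volunteer was included in the study without meeting the eligibility criteria", procedures done without written consent, two or more missing PK/PD blood samples, and "Any violation of the confidentiality of information about study participants". The section closes with the consequence: "In case of any major protocol deviations, the volunteer must be excluded from the final PK/PD data analysis".

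Section 9.7, which selects volunteers for analysis, sets other conditions: "Pharmacokinetics analysis will include data from volunteers who have received BCD-089 and have had no more than two missing/lost/damaged blood serum samples for pharmacokinetics". It adds a limit on consecutive missing samples and requires a pre-dose serum sample. The PD set is defined in a similar way. Deviations are not mentioned and 11.2 is not cited.

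Two other places bear on the point. Footnote 5 to section 4.7 says of eligibility deviations, "which are justified by the Investigator and agreed by the Sponsor, are not a reason to exclude the patient from the study". Section 6.6 calls a volunteer non-compliant when more than two PK/PD samples are missed.

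**The concern.** The rule in 11.2 contains no test of relevance. The definition of major joins rights, safety and data with an *or*, so a deviation touching only rights qualifies, and exclusion from PK/PD then follows automatically. A breach of confidentiality cannot change a serum concentration, yet once classed as major it removes the whole profile.

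Two sections also answer the same question differently. An analyst who follows 9.7 and one who follows 11.2 may report the primary PK and PD endpoints on different volunteers. The cohorts are so small that a single volunteer matters.

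**Working it through.** **Sample size.** The cohort table in section 9.2 on sample size gives cohort 01 one volunteer and cohorts 02 to 07 three each, with three more possible after a dose-limiting toxicity (DLT). The maximum is 1 + 6 × (3 + 3) = 37, which matches the synopsis. The mandatory number is 1 + 6 × 3 = 19. The usual cohort available for PK and PD is therefore three.

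**The two rules side by side**, for a dosed volunteer with a pre-dose sample:

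| Case | Section 9.7 | Section 11.2 |
|---|---|---|
| Complete profile, confidentiality breach | in | out if classed as major |
| Exactly two samples missing | in, since the limit is two | out if classed as major, and listed as probably so |
| Complete profile, sponsor-agreed eligibility deviation | in | out if classed as major |
| Complete profile, wrong dose given | in | out if classed as major |

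The first row shows 11.2 removing usable data. The second is a direct clash of thresholds, and section 6.6 sides with 9.7 because it also starts at more than two. The fourth row shows why deleting the 11.2 sentence is not enough: 9.7 on its own would keep a volunteer whose exposure is not that of his cohort.

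**Effect of losing one profile.** The standard error of a cohort mean is SD/√n.

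- From three to two: √(3/2) = 1.22 times larger.
- In a cohort expanded to six, from six to five: √(6/5) = 1.10 times larger.
- In cohort 01, from one to none: no PK/PD data at 0.06 mg/kg.

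As an illustration only, the t-based 95% half-width is t(0.975, n−1)/√n in SD units:

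- n = 3: 4.303/√3 = 2.48
- n = 2: 12.706/√2 = 8.98
- n = 6: 1.05
- n = 5: 1.24

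The ratio 8.98/2.48 = 3.6 splits into 1.22 from the standard error and 12.706/4.303 = 2.95 from the t multiplier on one degree of freedom instead of two.

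**How often.** The documents give no rate of major deviations unrelated to exposure. If the rate per volunteer were p, independent between volunteers, a cohort of three would lose at least one profile with probability 1 − (1 − p)³. For assumed rates of 2%, 5%, 10% and 20% this is 5.9%, 14.3%, 27.1% and 48.8%. These figures show how the loss scales with p. They do not predict the rate.

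**The case against.** Most items on the 11.2 list can affect concentrations or markers, and the list names only probable major deviations, so judgement remains at the classification step. The clearest irrelevant example, a confidentiality breach, should be rare. Section 5.3.1 allows replacement of volunteers who withdraw for unrelated reasons or are non-compliant under 6.6, so some losses can be made good. All of this stands and limits the size of the problem. It does not remove it: once a deviation is classed as major, exclusion is mandatory. Replacement is optional, and 5.3.1 does not expressly cover a confidentiality breach or an agreed eligibility deviation in a volunteer who completes the study.

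Four stronger readings are tempting and are not supported.

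- *Footnote 5 contradicts 11.2.* The footnote concerns exclusion from the study. A volunteer can stay in for safety and immunogenicity while his PK/PD data are dropped. The two texts are mismatched but not contradictory.
- *A volunteer just outside an eligibility limit, for example systolic pressure 122 against 100–120 mm Hg, would certainly be dropped.* That depends on classification, and 11.2 also has a minor category. Conversely, some eligibility criteria, such as earlier use of an antibody against IL-6 or its receptor, can bear on PK or PD.
- *Profiles could be selected after concentrations are known, because nothing fixes the timing of classification.* Sections 9.5 and 11.3 and most of 11.4 are redacted, so that absence cannot be asserted.
- *Precision falls 3.6-fold.* Most of that factor is the t multiplier, and section 9.2 on statistical methods names no confidence interval for a cohort mean. It plans descriptive statistics and rank tests.

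**Conclusion.** The point holds as a defect of wording with consequences for the primary PK and PD endpoints. Read literally, 11.2 can discard a valid profile for a reason unrelated to exposure. It also defines a different analysis set from 9.7, with an outright conflict at exactly two missing samples. For agreed eligibility deviations the conclusion is conditional: PK/PD data are lost only if the deviation is classed as major.

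Each such exclusion takes one of three volunteers from an unexpanded cohort and multiplies the standard error of the cohort mean by 1.22. In cohort 01 it removes the only profile. In a cohort expanded to six the effect is small. The total loss cannot be estimated, since no deviation rate is given. The safety set keeps every dosed volunteer, and DLT decisions rest on adverse events in the first seven days, so neither is affected.

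**What to change.** Define the PK and PD sets once, in section 9.7, and replace the last sentence of the 11.2 deviation rules with a reference to that definition. Section 9.7 should add:

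- *PK or PD data are excluded for a major deviation only if it can affect the concentrations or markers concerned. This is judged case by case, including for eligibility deviations agreed with the sponsor. The decision and its reason are recorded before the concentration results are reviewed.*
- *Data obtained without valid written consent are handled separately, on ethical grounds.*
- *A confidentiality breach alone does not lead to exclusion.*

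Use one missing-sample threshold in 9.7 and 11.2. Sections 9.7 and 6.6 already agree on more than two, so changing 11.2 to match is the smaller edit.

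The cost is wording in two sections and a short documented deviation review. No extra volunteers or samples are needed, and the planned numbers of 19 to 37 do not change.

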11.3. The Investigator’s responsibility for Protocol adherence

[REDACTED]

Translated from Russian to English, dated 06-Jul-2020

[REDACTED]

11.4. Study monitoring

The monitoring procedures for this study are established in accordance to Standard Operation Procedure of JSC BIOCAD.

[REDACTED]

11.5. Study termination

JSC BIOCAD may temporary or permanently stop the study due to issues related to safety, ethics, adherence to protocol, or other reasons. If necessary, JSC BIOCAD will undertake the necessary measures to inform the study site in advance. If the study is temporary or permanently closed, JSC BIOCAD and the Investigator must inform the Ethics Committees and regulatory

Translated from Russian to English, dated 06-Jul-2020

authorities. In such cases, all study-related data must be submitted to JSC BIOCAD and all unused study drugs must be returned.

12. ETHICS

12.1. Ethical aspects of the study

The study will be conducted in compliance with the ethical principles set forth in the World Medical Association's Declaration of Helsinki "International Ethical Guidelines for Biomedical Research Involving Human Subjects" 1964–2008 and ICH GCP rules.

[REDACTED]

12.2. Confidentiality of study subjects

The Investigator undertakes to maintain confidentiality regarding the identity of volunteers, the text of this Protocol, as well as all other materials and study results.

[REDACTED]

Translated from Russian to English, dated 06-Jul-2020

[REDACTED]

13.0. DATA MANAGEMENT AND RECORD KEEPING

All study-related documents must be archived at the study site or at the institution's central archive. The list of all study subject identification data must be carefully drafted.

According to ICH GCP definition, the required documents include: signed Protocol and all the amendments, copies of completed CRFs, signed Informed Consent Forms for all volunteers, medical records, diaries and other source documents, approved by ethics committees and regulatory authorities, as well as correspondence with them, including approved documents, drug accountability records, study-related correspondence and the list of volunteers names and addresses. This list is the essential document that should be kept by the Investigator.

The Investigator must keep copies of the required documents for 5 years.

At the end of this period, the Sponsor will inform the Investigator(s) about the date, after which this documents may be destroyed.

The study participant's documentation shall be archived in compliance with the study site rules.

The Investigator must inform the Sponsor about the place of storage of required documents and contact JSC BIOCAD for approval before destroying any of them. The Investigator must prevent accidental or premature destruction of these documents.

14. FUNDING AND INSURANCE

[REDACTED]

Translated from Russian to English, dated 06-Jul-2020

[Redacted content]

Translated from Russian to English, dated 06-Jul-2020

[REDACTED]

15. PUBLICATIONS

After the end of the study and statistical processing, its data will be published. The Investigator must not publish the results of this study, including those obtained at his/her study site, without consent from JSC BIOCAD. The results obtained at an individual study site should not be published prior to the publication of overall study results.
